Biologically active polysaccharides (BAP e.g., β -glucans - polymers of glucose commonly found in fungi, yeast, bacteria and cereals) represent one of the most studied natural immunomodulators with pluripotent biological effects (anti-infectious, antiviral, immunomodulatory). Selected molecules have an anti-inflammatory effect, inhibit the production of pro-inflammatory cytokines, and their preventing effect on lung damage was described in an animal model. By promoting the production of anti-inflammatory and regulatory substances, they restore balance in the cytokine network. The antiviral effect of BAP can be mediated either directly, through inhibition and/or disruption of viral particle integrity, or indirectly, by enhancing host antiviral defenses by supporting the body's immune processes. Other significant effects of β -glucans include their significant immunomodulatory effect (increasing the number of NK cells, stimulating phagocytic activity, promoting the development of antibody production, improving the post-vaccination response) and modulating effect on T-lymphocytes. The mechanism of action of β -glucans is mediated by several receptors, the most important is the Dectin-1 receptor.

Zinc application may also have a possible positive effect on the immune system, as several studies have suggested its effect in coronavirus infections. In vitro, zinc inhibits RNA-polymerase activity as well as virion replication. Vitamin D is also important for the functioning of the immune system, its positive effect has been observed in protection against infections (antibacterial effect, anti-inflammatory effect, differentiation of monocytes into macrophages), tumor diseases (anti-proliferative and antidifferentiation effect), and its deficiency may be a risk factor in the development of immunopathological reactions (autoimmune diseases).

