The efficacy and safety of food supplement Imunoglukan P4H[®] (pleuran, β -glucan from *Pleurotus ostreatus*, enriched with vitamin C) has been proven in numerous clinical studies and observations in children and adults, and it is therefore a suitable choice for supporting weakened immunity for both short-term and long-term use. Open-label and double-blind, placebo-controlled studies in children with recurrent respiratory infections confirmed the preventive effect of Imunoglukan P4H[®] on the incidence and intensity of recurrent bacterial and viral infections in children from 1 year of age. Imunoglukan P4H[®] has also shown the ability to induce changes in specific and non-specific cellular immunity parameters, which have reflected into a reduced incidence of respiratory infections in children and adults, prevention of immunosuppression induced by intense physical stress, and reduction of the incidence of infectious exacerbations in patients with chronic inflammatory diseases.

Supplementation with Imunoglukan P4H[®] was also able to achieve significant changes in markers of allergic inflammation in children (total IgE, blood eosinophil count), thus confirming previous results of in vitro tests, which indicated the anti-allergic potential of this active substance. Taking Imunoglukan P4H[®] supports physiological functions and maturation of the immune system in children and does not

cause its overstimulation. Imunoglukan P4H[®] ACUTE! (pleuran + vitamin C + zinc) confirmed its immunomodulatory effect in shortening the duration of symptoms in patients with herpes simplex virus type 1 (HSV-1) infection.

The results of clinical studies have confirmed the complex immunomodulatory effect of this preparation without any significant side effects.

Study design

It is a multicenter, prospective, randomized, double-blind, placebo-controlled study with a food supplement at an outpatient healthcare provider.

The investigators will enroll a total of **250 patients** who meet the inclusion criteria. The proposed study does not imply any change in pharmacological/non-pharmacological treatment, diagnostic interventions administered to enrolled subjects. In case the respiratory tract infections occur during the study period, the patient enrolled in the study will be treated according to standard management plan.

Patients will be randomized into 2 arms (active group and placebo group):

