- Active group: Imunoglukan P4H[®] chewable tablets (IMG[®] 50 mg + Zinc 5 mg + Vitamin D 10 μg in 1 tablet):
 - up to 25 kg of body weight 1 tablet once a day for 3 months
 - over 25 kg 2 tablets once a day for 3 months
 - Placebo group: Placebo chewable tablets (Zinc 5 mg + Vitamin D 10 μ g in 1 tablet)
 - o up to 25 kg of body weight 1 tablet once a day for 3 months
 - o over 25 kg 2 tablets once a day for 3 months

Discussion about design

Multicenter, prospective, randomized, double-blind, placebo-controlled study design is a perpective for obtaining clinically, scientifically and statistically significant results to elucidate the impact of the investigational product on primary and secondary endpoints. The 3-month duration of the study is justified in evaluating the modulation of the immune response and its clinical impact on such events as a reduction in the number of respiratory infections, shortening their duration, and reducing the need for ATB treatment. In addition to confirming the underlying hypothesis, the pilot study should also provide data on tolerability, safety and possible adverse effects.

Subjects enrolled in the study complete an anamnestic data collection and fill out relevant questionnaires during control visits.

Study endpoints

Primary endpoints – to evaluate the effect of pleuran administration (Imunoglukan P4H[®] chewable tablets) compared to the placebo group on reduction in the number of RTIs episodes (total number)

Secondary endpoints – to evaluate the effect of pleuran administration (Imunoglukan P4H[®] chewable tablets) compared to the placebo group on:

- reduction in the number of episodes of RTI subtypes
- reduction in the duration of RTI episodes (total duration, RTI subtypes)
- reduction of the need for antibiotic (ATB) therapy
- reduction of the number of missed days at school/nursery due to RTI
- reduction of the number of missed working days due to RTIs
- reduction of the number of emergency department visits due to RTI
- reduction of the number of physician visits due to RTI
- tolerability and safety

Inclusion criteria

- signed informed consent
- age 3-18 years
- history of recurrent respiratory infections:
 - Age 3 to 5 years (< 6 years): 6 or more upper or lower respiratory tract infections from October 2022 until the end of March 2023
 - Ages 6 to 18 years (≥ 6 years): more than 3 upper or lower respiratory tract infections from October 2022 until the end of March 2023

Exclusion criteria

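### Does a control tablet that contains zinc and vitamin D undermine the comparison of pleuran with placebo?

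*Combined protocol and SAP*

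**What the plan says.** Study design lists the two tablets. The active tablet holds IMG "50 mg + Zinc 5 mg + Vitamin D 10" μg, and the control is listed as "Placebo group: Placebo chewable tablets (Zinc 5 mg + Vitamin D 10" μg. The number of tablets by body weight and the three-month duration are the same in both arms.

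Study endpoints gives the primary aim as "to evaluate the effect of pleuran administration (Imunoglukan P4H[®] chewable tablets) compared to the placebo group", with the total number of RTI episodes as the outcome. The secondary endpoints use the same contrast. The study title names pleuran alone. Discussion about design, by contrast, refers to the impact of the investigational product.

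The Introduction says of zinc: "Zinc application may also have a possible positive effect on the immune system". Of vitamin D it says: "its positive effect has been observed in protection against infections". In the sentence on earlier evidence it describes Imunoglukan P4H as pleuran "enriched with vitamin C) has been proven in numerous clinical studies and observations in children and adults". Vitamin C does not appear in the list of tablet contents, and the abbreviation IMG is not explained.

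**The concern.** A placebo is normally taken to be inert. Here the comparator carries two ingredients that the plan itself regards as possibly active, and for vitamin D the claimed benefit lies in the same domain as the primary endpoint. The endpoint also places the branded tablet in parentheses after pleuran, as if the two were one thing. A reader could then take a null result to mean that the product does not work, or a positive result as the product's effect against nothing. The trial can show neither.

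Two further points add to the unease. If IMG brought vitamin C with it and the control did not, a difference between arms could not be credited to pleuran alone. And adverse effects of zinc or vitamin D would occur in both arms, so they would not show as a between-arm difference.

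**Working it through.** **Step 1: what differs between arms.** From Study design, per tablet:

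| Ingredient | Active | Control |
|---|---|---|
| IMG | 50 mg | none |
| Zinc | 5 mg | 5 mg |
| Vitamin D | 10 μg | 10 μg |

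Subtracting one column from the other leaves IMG. The contrast is pleuran given on top of zinc and vitamin D, if IMG is read as the pleuran component. The plan does not define IMG, so that reading is an assumption, though it is the natural one.

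**Step 2: does the contrast match the endpoint?** The endpoint's exposure is "to evaluate the effect of pleuran administration", and the title agrees. For that question the shared ingredients should be held equal, as they are. The parenthesis and the phrase in Discussion about design are loose, but no section plans a conclusion about the tablet against an inert one.

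**Step 3: does a zinc or vitamin D effect distort the result?** The documents give no event rate, effect size, alpha or power, so there is no planned figure to reproduce. All values here are assumptions. Let λ be the three-month RTI rate with no supplement, g the rate ratio for zinc plus vitamin D, and p the rate ratio for pleuran, with multiplicative effects.

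- Control rate = λg; active rate = λgp.
- Trial rate ratio = λgp / λg = p. The factor g cancels.
- Whole tablet against inert = gp, which this trial does not estimate.

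Power is approximated by Φ(|ln p| / SE − 1.96), with SE = √(1/(nλg) + 1/(nλgp)), Poisson variance and n = 125 per arm (250 patients split 1:1). With λ = 1.5 and p = 0.80:

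| g | Control rate | Active rate | Trial rate ratio | gp | Trial difference in episodes | Power |
|---|---|---|---|---|---|---|
| 1.0 | 1.50 | 1.20 | 0.80 | 0.80 | 0.30 | 53.1% |
| 0.9 | 1.35 | 1.08 | 0.80 | 0.72 | 0.27 | 48.9% |
| 0.8 | 1.20 | 0.96 | 0.80 | 0.64 | 0.24 | 44.5% |

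First row: SE = √(1/187.5 + 1/150) = √0.0120 = 0.1095; |ln 0.80| = 0.2231; 0.2231/0.1095 − 1.96 = 0.08; Φ = 53%.

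With λ from 1.0 to 2.0 and variance inflated by a factor of 1.0 to 1.5, power runs from 27% to 65% at g = 1.0 and from 23% to 56% at g = 0.8. The largest loss is 65.3% − 55.7% = 9.6 points, at λ = 2.0 without inflation.

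**Step 4: what would an inert control do instead?** If pleuran did nothing (p = 1.0) and g were 0.8 to 0.9, an inert control would give a rate ratio of 0.80 to 0.90, and pleuran would get credit for zinc and vitamin D. The matched control gives 1.0, the correct answer for pleuran.

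**Step 5: vitamin C.** The Introduction's vitamin C wording concerns the brand in earlier studies. The same section names another variant containing pleuran, vitamin C and zinc, so the brand covers more than one formulation. The trial tablet's own list has no vitamin C in either arm. An imbalance is possible only if IMG itself includes it, which the documents do not say.

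**Step 6: safety.** The visit plan records adverse events at V1, V2 and V3. The active arm's own rates therefore describe tolerability of the full tablet. Only attribution of harms to zinc or vitamin D through the between-arm difference is unavailable.

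**The case for a change.** The best argument for a change is that it would be cheap and would remove a real ambiguity. The plan does not say that pleuran is being added to zinc and vitamin D, it calls a possibly active tablet a placebo, and it leaves IMG undefined. Under the assumptions above, a trial rate ratio of 0.80 would be compatible with 0.64 to 0.72 for the whole tablet against inert if zinc plus vitamin D cut RTIs by 10 to 20%, so the two readings are not interchangeable.

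All of that stands as a description. It does not show an error in the trial. The 0.64 to 0.72 range belongs to a contrast that the endpoint's main wording does not name, and the 10 to 20% behind it has no source in the documents. Misreading by others is a prediction about readers, and the control's composition is printed in the arm description for anyone who reports or appraises the result. The vitamin C point remains conditional. If IMG did contain vitamin C, the result would have to be credited to pleuran plus vitamin C, but the arms and the analysis would be the same.

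**Conclusion.** The concern does not call for a change. The control is matched to the active tablet on every listed ingredient except IMG, which is the correct comparator for the effect of pleuran. The comparison of randomized groups is not biased by the shared zinc and vitamin D. Under multiplicative effects the rate ratio is unaffected; if pleuran interacts with zinc or vitamin D, the trial still validly estimates its effect in children taking both. The price is a smaller absolute difference and up to about 10 points of power in the assumed grid, a fair trade for isolating the component under study.

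The remaining gap is one of labelling, which a competent report fills by stating the content of both tablets and confining between-arm conclusions, including those on safety, to what pleuran adds. Rewriting the endpoint would leave every arm, analysis and result as it is. This conclusion rests on reading IMG as pleuran and on the arm lists being complete, with no vitamin C difference between tablets.

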- refused informed consent
- bronchopulmonary dysplasia
- primary immunodeficiency
- cystic fibrosis
- chronic diarrhoea
- chronic diseases of the lungs, kidneys and liver
- malformations of the cardiovascular system
- oncological disease
- malnutrition
- intolerance to any of the ingredients in the study product
- taking preventive immunomodulatory therapy (beta-glucans, bacterial lysates, isoprinosine) less than 14 days prior enrolling the patient into the study

List of data collected from study subjects

Basic identification data	• Patient ID				
	 Patient Initials 				
	 Patient's Date of birth 				
	 Date of completion of CRF / Date of visit 				
Medical history and	o Age				
demographics	o Sex				
	 Current comorbidities 				
	 Current treatment of comorbidities 				
Diagnostic procedures	 Patient diary (Respiratory infections) 				
Primary endpoints	 RTIs incidence (total) 				
Secondary endpoints	 RTIs subtypes incidence 				
	 Duration of RTIs (total duration, RTIs subtypes) 				
	 The need for ATB therapy for the treatment of RTIs 				

	0	Number of missed days in school/nursery due to RTIs		
	0	Number of missed working days due to RTIs of the child		
	• Number of Emergency department visits due to			
	0	Number of Physician visits due to RTIs		
	0	Tolerability		
	0	Safety (occurrence of adverse events)		
Other data	0	Compliance		

Study visit and evaluation plan

Visit number	V0	V1	V2	V3
Day of visit	Initial	after 1 st month	after 2 nd month	after 3 rd month
	examination	(30 ±7 days)	(60 ±7 days)	(90 ±14 days)
Informed consent	Х			
Inclusion / exclusion	х			
criteria				
Demographics	Х			
Medical history	х			
Comorbidities	х	х	Х	х
Dispensing of study product	Х			
Incidence of respiratory tract infections (Patient diary)		Х	Х	х
Adverse events		Х	х	х
Returning the study product, product accountability and patient compliance				х

Required diagnostic procedures

Patient diary "Respiratory tract infections"

Parents or legal representatives of study subjects will record up-to-date data (incidence of infectious morbidity, symptoms, need for ATB therapy, physician or emergency department visits, number of missed days at school/nursery and work due to RTIs) throughout the study period. The filled "Patient diary" will be handed over to the treating physician at each visit.

Adverse event form

The physician fills out the Adverse event form when adverse events occur and records the occurrence of adverse events also in the CRF.

Compliance

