Study subjects will return the container with remaining study medication at V3 (visit after 3 months) to their treating physician, who will count the number of remaining tablets. The physician will record the result in CRF. Patients with <75% compliance will be excluded from the study due to lack of collaboration.

Appendices to the study protocol, other changes in the conduct of study

Any amendments to the Protocol will be made in the form of an Appendix to the Protocol. Changes to the study are not permitted. Any unexpected and sudden changes in the conduct of study will be recorded in the clinical report.

Privacy Policy

All patients in this study will be identified with a unique ID. Identification of the patient through this ID will not be possible. Only the monitor can validate the source data. The unique ID of a particular patient will only be known to the investigator or monitor. The personal identification data entered into this study will be: date of birth, gender and initials. The nature of personal data identifiers is governed by all relevant legislative requirements.

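### The end-of-study compliance rule drops randomised children whose diary outcome is already known

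*Combined protocol and SAP*

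**What the plan says.** All references are to the combined protocol and SAP.

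- **Study endpoints:** the primary comparison is the effect of pleuran "compared to the placebo group on reduction in the number of RTIs episodes (total number"). The list of data collected names the same endpoint "RTIs incidence (total"), with no time unit.
- **Required diagnostic procedures:** the outcome comes from a diary kept by the parents. It covers "incidence of infectious morbidity, symptoms, need for ATB therapy, physician or emergency department visits", as well as missed days, and it "will be handed over to the treating physician at each visit".
- **Study visit and evaluation plan:** "Dispensing of study product" is marked at V0 only. Product return, accountability and compliance are marked at V3 only.
- **Compliance:** "Study subjects will return the container with remaining study medication at V3 (visit after 3 months"), and the physician counts what is left. Then: "Patients with <75% compliance will be excluded from the study due to lack of collaboration". No exception is made for children whose diary is complete.
- **List of data collected:** each record carries "Date of completion of CRF / Date of visit".

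The document as supplied has no statistical section. It names no analysis set, model, significance level, or expected rates of infection, dropout or non-compliance.

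**The concern.** The 75% rule is the only statement in the plan about which randomised children count, and it depends on behaviour after randomisation. The tablet count and the diary are separate sources, so failing one says nothing about whether the other is available. A child who attends V3 with three months of diary pages and more than a quarter of the tablets left has a known primary outcome, and the rule discards it.

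Tablet-taking could be related to infection: a sick child may skip tablets, or a well child's family may lose interest. It could also be related to tolerability, which the trial is itself measuring. If such links act differently in the two arms, the retained children are not comparable, and part of any difference in RTI counts reflects who was removed. For children with full diaries this risk is entirely avoidable.

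**Working it through.** **Step 1: what the rule does in practice.** Compliance is first known at V3, planned at 90 ± 14 days. V3 is also the completion visit. Exclusion at that point cannot alter treatment or follow-up; its only practical effect is on whose data are used.

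**Step 2: size of a possible bias.** The plan gives no figure to reproduce here. From the documents: 250 children, 1:1, so 125 per arm. Assumed: no true effect; a share *a* (active) and *p* (placebo) excluded; excluded children have *k* times the infection rate of the others; both arms have the same overall rate.

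The retained children's mean is the overall mean divided by (1 − share + k × share), so the apparent active/placebo ratio is

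(1 − p + kp) / (1 − a + ka).

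| Excluded, active v placebo | k | Ratio among retained |
|---|---|---|
| 15% v 5% | 2 | 1.05/1.15 = 0.913 |
| 5% v 15% | 2 | 1.15/1.05 = 1.095 |
| 5% v 15% | 1 | 1.000 |
| 5% v 15% | 0.5 | 0.925/0.975 = 0.949 |
| 5% v 10% | 0.5 | 0.950/0.975 = 0.974 |
| 5% v 10% | 2 | 1.10/1.05 = 1.048 |
| 10% v 10% | same in both arms | 1.000 |
| 10% v 10% | 1 active, 2 placebo | 1.10/1.00 = 1.10 |

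Negative binomial simulation agrees: 0.909 for the first row, 1.093 for the second, and 0.971 to 1.050 for 5% v 10%.

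**Step 3: compare with sampling error.** Assume a mean of 2 episodes per 90 days (125 × 2 = 250 per arm) and dispersion 0.3. The standard error of the log ratio is √[2 × (1/250 + 0.3/125)] = √0.0128 = 0.113 with nobody lost, and 0.114 to 0.123 in simulation with losses. The largest shift at 15% v 5% is |ln 0.913| = 0.091, which is 0.8 of a standard error. The last row gives ln 1.10 = 0.095, also below one.

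For the first row, the chance of a false claim for the active arm (nominal 2.5%) is about Φ(−1.96 + 0.091/0.12) = Φ(−1.20) = 11.5%. Simulations of 1,500 and 3,000 runs gave 10.3% and 13.1%.

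**Step 4: keep the same children.** With full diaries and everyone analysed as randomised, the 3,000-run simulation gave a ratio of 0.996 and 3.0% false claims for the active arm.

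**Step 5: early leavers kept in the wider set.** Take leaving at day 30, 15% v 5%, k = 2. Raw totals gave 0.881; a log(days observed) offset gave 0.956. At day 60 the figures were 0.942 and 0.983. Across both directions of imbalance and k from 0.5 to 2, the offset results ran from 0.956 to 1.043. If leavers have half the others' rate (5% v 15%), the offset's error (0.975-0.987) is similar in size to that of raw totals (1.017-1.040), in the opposite direction. The offset helps but is not a cure.

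**The case against.** **The rule says excluded from the study, not from the analysis.** True, and removal from the analysis is an inference. But at V3 no other practical effect remains, and no analysis set says otherwise.

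**The sizes are assumed.** This stands. The larger figures need a 10-point difference between arms, or excluded children who differ in kind by arm, in a double-blind trial whose tablets share zinc and vitamin D. No document figure supports either. The point should rest on the avoidable loss of known outcomes, not on the 10-13% error rate.

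**Analysing only children with diary data is also a post-randomisation selection.** True. It is a smaller one, because it drops only children with no outcome data.

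Two stronger readings are tempting, and the documents do not support them.

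- *That the plan has chosen to analyse raw totals with no allowance for time observed.* It only names an endpoint, a count over a nominal common three months, and elsewhere calls it incidence. No analysis is stated, so this is silence, not a wrong method. The V3 window (days 76 to 104) is minor: if visits are spread evenly over it, it adds 0.9-2.6% to the variance for means of 1-3 episodes and dispersion 0-0.5, balanced between blinded arms.
- *That every early leaver is excluded.* Measured against a full course, stopping before 0.75 × 90 = 67.5 days fails the rule. But the denominator is not stated, and a child who never reaches V3 may have no count at all. The text does not settle what happens to these children.

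**Conclusion.** The concern holds for children with diary data who fail the tablet count. Followed as written, the rule removes randomised children with known outcomes, and the comparison loses the protection of randomisation for no gain in data quality.

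Whether bias follows is unknown. Under no true effect and assumed rates, the ratio moves to 0.91 or 1.10 when exclusion is 15% v 5% or the reverse with k = 2, and to 0.97-1.05 at 5% v 10% with k from 0.5 to 2. It stays at 1.00 when equal shares of similar children are excluded. All shifts are about one standard error or less. A reader might infer that the trial's result is biased in favour of the product; nothing in the documents shows a difference between arms or its direction. This is a point that should be corrected, not one that invalidates the design. Confidence is medium because every rate is assumed.

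**What to change.** 1. Make the primary analysis include all randomised children with diary data, by assigned arm and whatever their compliance.
2. Use the 75% rule only to define a per-protocol sensitivity analysis, and state its denominator (tablets for the full course, or for days on study).
3. Compare arms by rate ratio in a count model, for example negative binomial, with a log(days observed) offset running from V0 to the last diary return. This stops early leavers entering with truncated totals. The visit dates already collected are enough; no day-90 cut-off or new diary field is needed.
4. Report by arm how many children had under 75% compliance, left early, or had no diary data.

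Cost: analysis wording, issued as an Appendix to the protocol. The section on appendices names that route for amendments but also says that changes to the study are not allowed, so the sponsor should record this as a clarification of the analysis, fixed before unblinding. No visit, product or clinical procedure changes.

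Downsides: the compliance-restricted result becomes secondary, children with no diary return still contribute nothing, and the offset reduces but does not remove bias if leaving is tied to infection rate.

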Respiratory infections are characterized by both microbial load, respiratory epithelium response, and activation of inflammation and immune responses. These aspects lead to structural and functional changes in the respiratory tract. There is an overgrowth of goblet-shaped glands, which leads to excessive production of hyperviscous mucus. There is a weakening of mucociliary clearance, either due to the direct toxic influence of microorganisms on cilia and their oscillation, but also indirectly through an increase in the viscosity of mucus in the lumen of the respiratory tract. Respiratory epithelial cells form many pro-inflammatory and chemotactic compounds that lead to the development of inflammatory infiltrate in the airways. This is accompanied by oxidative stress, which impairs both the structure and function of biomolecules. Inflammation subsequently increases the reactivity of cough receptors. All these factors cause clinical signs of respiratory infections, whether from the respiratory tract (cough, expectoration, obstruction with wheezing, bronchial hyperreactivity, congestion and runny nose) or at the level of the whole organism (increased body temperature, weakness, myalgia and fatigue).

Recurrent respiratory tract infections (RRTIs)

RRTIs are a separate category of RTIs and represent a typical medical problem of preschool and school age. They can be defined on the basis of several aspects as infectious respiratory diseases, in which other more serious causes have been excluded (cystic fibrosis, primary immune disorders, congenital ciliary dyskinesias, respiratory malformations). Most children with RRTIs do not suffer from severe immunodeficiency and the high frequency of respiratory infections is due to a combination of various factors (immaturity of the immune system, high exposure to infectious agents in the family or children's collective, environmental factors, adenoid hypertrophy, etc.). In addition, allergic inflammation in the airways may also contribute to increased susceptibility to RTIs.

According to data from epidemiological studies, approximately 6-10% of children between 2-6 years of age suffer from RRTIs. Due to their high incidence, RRTIs have an important socio-economic impact (affecting quality of life, missed school days, missed days at work, repeated medical examinations, hospitalization, as well as increased antibiotic prescription).

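### Missed school/nursery days and missed working days are raw counts with no record of who could lose a day, which dilutes the difference in days and costs power

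*Combined protocol and SAP*

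**What the plan says.** The section Study endpoints lists "reduction of the number of missed days at school/nursery due to RTI" and "reduction of the number of missed working days due to RTIs" among the secondary endpoints. The section List of data collected from study subjects carries them as "Number of missed days in school/nursery due to RTIs" and "Number of missed working days due to RTIs of the child". Under Required diagnostic procedures, parents record in the diary the "number of missed days at school/nursery and work due to RTIs".

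The history and demographics row of the data list has four items: age, sex, comorbidities, and "Current treatment of comorbidities". No item covers nursery or school attendance, scheduled days, or a carer's work. The inclusion criteria ask for consent, age 3-18 and a history of recurrent infections. None requires attendance or a working carer.

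For these two endpoints the protocol gives no denominator, no rule for children to whom the item does not apply, and no statistical method. The diary and CRF forms are not reproduced. The section Discussion about design also says that subjects "fill out relevant questionnaires during control visits", without describing the content.

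**The concern.** A four-year-old kept at home cannot miss nursery, and a carer without paid work cannot miss a working day. If such children enter the count, they score zero however often they are ill. Age does not resolve this: a child of 3-5 years may or may not attend nursery, and carers' employment cannot be read from the child's age.

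These zeros carry no information about treatment. They reduce the difference in mean days, which is the figure an economic reader would use, and they add ties to a rank test. Attendance may also be prognostic on the protocol's own account: its background on recurrent infections names "high exposure to infectious agents in the family or children's collective" as a contributor to infection frequency. If status is not recorded during the trial, it can be recovered only by later recall.

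**Working it through.** **Inputs.** From the protocol: 250 children allocated 1:1, so 250/2 = 125 per arm before any exclusions. It states no alpha, power, effect size, SD or test for any endpoint, so there is no figure to reproduce. Everything else below is assumed: the share q of children who cannot lose a day (equal in both arms), the means, the spread, and a two-sided 5% test.

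**Step 1: dilution.** Each arm's mean becomes (1 − q) × at-risk mean.
- Difference = (1 − q)(μ₀ − μ₁). With 5 versus 3 days, 2.0 becomes 1.8 at q = 10%, 1.6 at 20% and 1.4 at 30%.
- Ratio = (1 − q)μ₁ / [(1 − q)μ₀] = 3/5 = 0.60 at every q.

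**Step 2: comparison of means, by formula.** Take an at-risk mean of 6 and SD of 6, with the difference set for 80% power at q = 0: d = (1.96 + 0.84) × 6 × √(2/125) = 2.13. With q > 0, variance = (1 − q)s² + q(1 − q)m², where m = 6 − 2.13/2 = 4.94.

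At q = 20%:
- All children: difference 0.8 × 2.13 = 1.70; SD = √(0.8 × 36 + 0.16 × 4.94²) = 5.72; standard error = 5.72 × √(2/125) = 0.72; power 65%.
- At-risk only: 100 per arm; standard error = 6 × √(2/100) = 0.85; power 71%.

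| q | All children | At-risk only |
|---|---|---|
| 5% | 77% | 78% |
| 10% | 73% | 76% |
| 20% | 65% | 71% |
| 30% | 57% | 65% |
| 40% | 49% | 58% |

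**Step 3: simulation by type of test.** Negative binomial counts, dispersion 1, means 5 versus 3, 125 per arm. Repeat runs agree to within about 2 points.

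| q | Rank test: all / at-risk | Means: all / at-risk |
|---|---|---|
| 10% | 75% / 84% | 90% / 93% |
| 20% | 59% / 79% | 84% / 90% |
| 30% | 44% / 74% | 74% / 83% |

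With means of 6 versus 4.1, the rank test gives 67% at q = 0, then 50% / 60% at q = 10%, 38% / 56% at 20% and 27% / 51% at 30%. Restriction therefore recovers part of the loss. The rest comes from having fewer informative children and cannot be recovered.

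**Step 4: imbalance and error rate.** The SD of the between-arm difference in q is √(2q(1 − q)/125): 3.8 points at q = 10% and 5.1 points at q = 20%. In null simulations with 0-30% structural zeros, the rank test's type I error was 4.5-5.7%.

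**The case against.** Several stronger readings are tempting, and the documents do not support them.

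- **That every child is counted and scored zero.** A reader might infer this from the bare counts, but the protocol is silent on the denominator. The unseen diary, history-taking or questionnaires might allow a not-applicable answer. What stands is that the itemised data list shows no such item. The questionnaires are described for control visits, whereas a baseline-defined set needs status at V0.
- **That any effect is masked.** It is attenuated. At q = 20% a comparison of means still has 84% power under the inputs of Step 3, and the ratio of means does not move. The large losses belong to the rank test, and the protocol names no test.
- **That chance imbalance would pass for an effect.** Randomisation balances these children on average, and the test's error rate already covers the remainder.
- **That these are the only socio-economic endpoints.** The background section also counts repeated examinations, hospitalisation and antibiotic prescribing in that impact. Antibiotic need and physician and emergency visits are separate secondary endpoints that do not depend on attendance or employment.
- **That a teenager at home alone is a further case.** If the carer works and loses no day, that is a true zero for this endpoint. Restricting to working carers would rightly keep the child.

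Two further points have weight. Average days lost per enrolled child is a legitimate quantity, and restriction answers a different question. Infection counts and durations are recorded per child, so an ill child with no missed days is visible. That still does not show whether the child had a day to lose.

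**Conclusion.** The concern holds as a loss of precision and interpretability on two secondary endpoints. The listed data would not let an analyst separate the two kinds of zero. The difference in days shrinks by the share q. Restricting to at-risk children would raise power at q = 20% by about 6 points for a comparison of means (84% to 90%) and about 20 points for a rank test (59% to 79%), under the assumed 5 versus 3 days and dispersion 1. At q = 10% the gains are about 3 and 9 points.

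The share itself is not in the documents. It may well differ between the two endpoints: non-attendance probably matters mainly at ages 3-5 (an assumption), while a carer's work status can matter at any age. There is no bias in the ratio of means, no inflation of type I error, and no effect on the primary endpoint. This is a worthwhile, inexpensive improvement and not a threat to the trial's main conclusion.

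**What to change.** - At V0, before allocation, record whether the child attends school or nursery (yes/no) and whether a carer who would stay home is in paid work (yes/no).
- Add a not-applicable code to the two diary items, and state whose working days count.
- Analyse missed school/nursery days among children attending at V0, and missed working days among children with a working carer at V0. Both sets are fixed before treatment, so the comparison stays randomised.
- Report the at-risk number per arm, and give the all-children count as a supporting analysis.

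The cost is two tick-box items at a visit that already takes demographics, one diary code, and a sentence per endpoint. The price in interpretation is a smaller N for these two endpoints and results that describe at-risk families, not all enrolled families. The supporting analysis covers the latter.
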